14.9 MISSING DATE INFORMATION FOR CONCOMITANT MEDICATIONS

For concomitant medications, incomplete (ie, partial missing) start date and/or stop date will be imputed. When the start date and the stop date are both incomplete for a subject, impute the start date first.

Incomplete Start Date

The following rules will be applied to impute the missing numerical fields. If the stop date is complete and the imputed start date is after the stop date, then the start date will be imputed using the stop date.

Missing day and month

- If the year of the incomplete start date is the same as the year of the date of the first dose of study drug, then the day and month of the date of the first dose will be assigned to the missing fields.
- If the year of the incomplete start date is before the year of the date of the first dose of study drug, then December 31 will be assigned to the missing fields.
- If the year of the incomplete start date is after the year of the date of the first dose of study drug, then January 1 will be assigned to the missing fields.

Missing month only

• The day will be treated as missing and both month and day will be replaced according to the above procedure.

Missing day only

- If the month and year of the incomplete start date are the same as the month and year of the date of the first dose of study drug, then the day of the first dose will be assigned to the missing day.
- If either the year is before the year of the date of the first dose of study drug or if both years are the same but the month is before the month of the date of the first dose of study drug, then the last day of the month will be assigned to the missing day.
- If either the year is after the year of the date of the first dose of study drug or if both years are the same but the month is after the month of the date of the first dose of study drug, then the first day of the month will be assigned to the missing day.

Incomplete Stop Date

For the purpose of deriving a concomitant medication flag, the following rules will be applied to impute the missing numerical fields. If the date of the last dose of study drug is missing, impute it as described in Section 14.5. If the imputed stop date is before the start date (imputed or non-imputed start date), then the imputed stop date will be equal to the start date.

Missing day and month

- If the year of the incomplete stop date is the same as the year of the date of the last dose of study drug, then the day and month of the date of the last dose will be assigned to the missing fields.
- If the year of the incomplete stop date is before the year of the date of the last dose of study drug, then December 31 will be assigned to the missing fields.
- If the year of the incomplete stop date is after the year of the date of the last dose of study drug, then January 1 will be assigned to the missing fields.

[figure not shown]
Missing month only

• The day will be treated as missing and both month and day will be replaced according to the above procedure.

Missing day only

- If the month and year of the incomplete stop date are the same as the month and year of the date of the last dose of study drug, then the day of the last dose will be assigned to the missing day.
- If either the year is before the year of the date of the last dose of study drug or if both years are the same but the month is before the month of the date of the last dose of study drug, then the last day of the month will be assigned to the missing day.
- If either the year is after the year of the date of the last dose of study drug or if both years are the same but the month is after the month of the date of the last dose of study drug, then the first day of the month will be assigned to the missing day.

[figure not shown]

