6.1 Overall Study Design

This is a phase 2 open label safety study of GLYX-13 for participants who completed 12 weeks of treatment in GLYX13-C-202 (NCT01684163).

At the screening visit, the Structured Clinical Interview for Depression (SCID) will be administered to determine whether any exclusionary conditions have arisen since subject's completion of GLYX13-C-202. A physical examination will be conducted to ascertain if significant changes have occurred since the subject ended participation in GLYX13-C-202. Blood and urine samples will be obtained for laboratory analysis. Antidepressant agents used since the subject ended participation in GLYX13-C-202 will be recorded.

On Week 1, subjects will arrive at the investigative site having fasted for at least 10 hours, with water as desired. Each subject's eligibility will be confirmed; then a physical examination will be performed, and blood and urine samples for laboratory analysis will be obtained. Vital signs will be assessed and mass recorded. ECG will be recorded,

Each subject will then receive an IV dose of rapastinel (GLYX-13), 225 mg or 450 mg (replaces 5 mg/kg or 10 mg/kg, respectively) in a "slow bolus" injection in an upper extremity vein within approximately 1 to 2 minutes. Subjects will be discharged following determination by the investigator that they are medically able to leave.

ECG will be recorded and blood and urine samples will be obtained for laboratory analysis. Rapastinel (GLYX-13) will be administered. Subjects will remain in the study unit until determination by the investigator that they are medically able to leave.

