5.1 PROTOCOL DEVIATIONS

The number and percentage of subjects with significant protocol deviations will be summarized overall for the Safety Population. Protocol deviations will be defined, including significance classification, in the Protocol Deviation Requirement Specification.

6.0 DEMOGRAPHICS AND OTHER BASELINE CHARACTERISTICS

Demographic parameters (age, sex, ethnicity, race, weight) and other baseline characteristics will be summarized overall for the Safety Population.

Medical and surgical history, and psychiatric history will be summarized overall for the Safety Population. *Prior medication* will be defined as any medication started before the date of first dose of study drug. *Concomitant medication* will be defined as any medication taken on or after the date of first dose of study drug.

The use of prior medication will be summarized by the number and percentage of subjects receiving each medication within each therapeutic class and overall for the Safety Population. Concomitant medications will be summarized by the number and percentage of subjects receiving each medication within each therapeutic class and overall for the Safety Population. Multiple medication use of the same therapeutic class by a subjects will only be counted once. Prior and concomitant psychotropic medication, as well as any medications for the treatment of depression will be summarized for Safety Population.

The WHO Drug Dictionary Enhanced, will be used to classify prior and concomitant medications by therapeutic class and drug name.

7.0 EXTENT OF EXPOSURE AND TREATMENT COMPLIANCE

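### SAP 14.9 can count a drug that ended before entry as Concomitant and not Prior when its start date lacks the month and its stop date is also partial

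*SAP*

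**What the plan says.** SAP section 6.0 separates two classes. The Prior class covers "any medication started before the date of first dose of study drug". A drug belongs to the Concomitant class if it was used at any time from the first-dose date onward. Both are tabulated for the Safety Population, and psychotropic drugs and drugs for depression are also summarized in their own right.

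SAP section 14.9 completes partial medication dates. Four of its rules matter here:

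- **Start, day and month missing, same year as first dose:** "then the day and month of the date of the first dose will be assigned to the missing fields". A start with only the month missing is handled the same way.
- **Safeguard on the start:** the start is reset to the stop date, but under a condition: "If the stop date is complete and the imputed start date is after the stop date".
- **Order:** "When the start date and the stop date are both incomplete for a subject, impute the start date first".
- **Stop:** a year-only stop in the last-dose year becomes the last-dose date. For a year-only stop in an earlier year, "then December 31 will be assigned to the missing fields". A stop with only the day missing, in a month before the last-dose month, becomes the last day of its month. An imputed stop that falls before the start is moved forward to the start.

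On collection, Protocol section 6.1 says of the screening visit: "Antidepressant agents used since the subject ended participation in GLYX13-C-202 will be recorded". Protocol section 7.2.3 also asks for drugs taken in the current episode to be documented relative to Screening.

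**The concern.** A start date equal to first dose fails the Prior definition and meets the Concomitant one, so the imputation settles the classification. It does so without using two facts that may already be on file: that the drug was recorded before any study drug was given, and that the recorded stop month lies before the first-dose month. When both dates are partial, the start is fixed first and the stop is then moved forward to it, so a known stop month can be overwritten.

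At stake is whether the medication tables describe background therapy correctly. An antidepressant that ended before entry could appear as taken alongside rapastinel and be absent from the prior-medication table. The protocol asks for interval antidepressants specifically, so these are records that a reader of the tables would look for.

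**Working it through.** The documents give no figure on this point. The check applies the SAP 14.9 rules and the SAP 6.0 definitions to assumed dates.

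**Assumed inputs:** first dose 15 Jun 2015; screening 14 days earlier, 1 Jun 2015; last dose either 1 Dec 2015 or 1 Mar 2017; start recorded only as 2015; true start before screening.

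**Rules applied:** Prior = imputed start < first dose. Concomitant = drug ongoing, or stop ≥ first dose.

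| Recorded stop | Start used | Stop used | Prior | Concomitant | Error |
|---|---|---|---|---|---|
| 20 Mar 2015 (complete) | 20 Mar 2015 | 20 Mar 2015 | yes | no | none |
| 1 Sep 2015 (complete) | 15 Jun 2015 | 1 Sep 2015 | no | yes | Prior lost |
| ongoing | 15 Jun 2015 | none | no | yes | Prior lost |
| Mar 2015 (day missing) | 15 Jun 2015 | 31 Mar, moved to 15 Jun 2015 | no | yes | both wrong |
| 2015 only, last dose 1 Dec 2015 | 15 Jun 2015 | 1 Dec 2015 | no | yes | both wrong if the drug ended before first dose |
| 2015 only, last dose 1 Mar 2017 | 15 Jun 2015 | 31 Dec 2015 | no | yes | both wrong if the drug ended before first dose |

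The Mar 2015 row comes out the same for either last-dose date. The imputed stop of 31 Mar falls before the imputed start of 15 Jun, so the stop becomes 15 Jun.

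**Enumeration.** Take every true start from 1 Jan to 1 Jun 2015 (152 days) and every true stop from that start to 14 Jun (day 165 of the year), with last dose 1 Mar 2017. The number of pairs is the sum of (166 − a) for a = 1 to 152, which is 152 × 166 − (152 × 153)/2 = 25,232 − 11,628 = 13,604. All of these drugs began before screening and ended before first dose, so the right answer is always Prior and not Concomitant.

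- Stop recorded in full: 0% misclassified.
- Stop recorded as month and year: 100% lost from Prior, 100% counted as Concomitant.
- Stop recorded as year only: 100% and 100%.

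These percentages describe the rule given that pattern of missing dates. They say nothing about how common the pattern is.

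**The case against.** Four points can be made for the plan.

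1. **It is a consistent convention.** SAP section 14.8 gives adverse events the same first-dose default, and the default leans toward counting ambiguous use as on treatment. This stands where the record is truly ambiguous, such as a drug first reported after dosing. It does not justify overriding evidence that the drug was in use, or finished, before dosing.
2. **Section 14.9 is headed for concomitant medications**, and its stop rules are said to serve the concomitant flag. So its use for Prior is inferred. That stands as a caution, but it is the only medication date rule shown. Prior status either follows it or has no rule, and the false Concomitant flag arises either way.
3. **The affected set is narrow.** False Concomitant status needs a start without a month in the first-dose year, a partial stop, and true stopping before first dose. This stands. Nothing in the documents suggests that recent antidepressants asked about at screening would commonly lack a month.
4. **The tables may hide it.** Subjects are counted once per therapeutic class, so a record-level error need not change a subject-level count. This also stands.

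A reader might infer that pre-entry drugs in general drop out of the Prior table. They do not: a complete stop date before first dose protects the record. A reader might also infer that interval antidepressants often fall in the first-dose year, or that the safety results are distorted. The documents give no source for the first. On the second, the primary endpoint counts subjects with adverse events, and no safety analysis shown is split or adjusted by medication.

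**Conclusion.** Wrong as written, and minor. For a start with no month in the first-dose year, SAP 14.9 discards information that can settle the class:

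- If the stop is also partial, a drug that ended before entry is not Prior and is counted as Concomitant. In the month-and-year case this contradicts the recorded stop month.
- If the drug continued past first dose, Concomitant is correct and only Prior status is lost.
- If a complete stop date precedes first dose, the result is correct.

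The effect is confined to the descriptive prior and concomitant medication tables, including those for psychotropic and depression drugs. The number of affected records cannot be obtained from the documents. It is tempting to size the problem by the share of the year before first dose. With first dose on 15 June and starts spread evenly, that is 165/365 = 45.2%. The same reasoning gives 0% for 1 January and 364/365 = 99.7% for 31 December, and it includes drugs that are rightly Concomitant. It is not an error rate.

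The conclusion rests on reading 14.9 literally, on assumed dates for the example, and, for Prior, on 14.9 being the rule that applies.

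**What to change.** Amend SAP section 14.9 as follows:

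1. State that its date rules apply to both Prior and Concomitant classification.
2. For a drug recorded before first dose as in use or already stopped, the imputed start may not be later than the day before first dose.
3. If the drug was recorded then as stopped, or if its known stop month or year precedes that of first dose, the imputed stop may not be later than the day before first dose, and the imputed start may not be later than the imputed stop. This takes precedence over the rule that sets the stop equal to the start.
4. Keep the present rules for drugs first reported after first dose, apart from the known-stop-month-or-year condition in item 3.

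The cap must be the day before first dose and not the visit date, because a stop on Day 1 still meets the Concomitant definition.

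Applied to the example, stop Mar 2015 gives stop 31 Mar and start 31 Mar: Prior, not Concomitant. A year-only stop recorded at screening as stopped gives 14 Jun for both dates: Prior, not Concomitant. An ongoing drug recorded at screening gives start 14 Jun: Prior and Concomitant.

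The cost is a small programming condition. The partial-stop rule needs no extra data. The pre-dose rule needs the collection visit or a pre-dose flag on the medication record. The documents do not show whether the eCRF carries one, so that rule applies where it does.

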18.0 HISTORY OF CHANGES

Date	Section	Description
12/11/2018	NA	Initial version approval.
